6. STUDY DESIGN

This is a prospective, single arm, non-randomized, multi-center observational study to record objective data in patients undergoing upper extremity arteriovenous fistula construction with autologous tissue for the purpose of eventual hemodialysis access, in whom the EchoMark implantable marker is placed at the site of vascular anastomosis and the EchoSure module is used to collect ultrasonic data.

The expected duration of this study will be from May 2020 to December 2021. Patients will be identified and recruited by the surgeons participating in the study, who will be determined at a later date. Patients who have been scheduled for creation of an upper extremity autologous arteriovenous fistula creation surgery will be identified as appropriate for study recruitment. The study details will be explained to identified patients and the consent process will begin for willing patients. Participants in the study will have EchoMark devices implanted at the time of the surgery. Monitoring of fistulae will be performed in the postoperative period. Patients who wish to terminate their participation in the research will no longer receive EchoSure ultrasound examinations of their fistula and will revert to the standard monitoring practice of their surgeon.

Stage 1: Patients will be monitored using the EchoSure ultrasound to collect data. Data will be analyzed in an attempt to formulate normative ranges for relevant variables such that clear, objective metrics consistent with healthy versus pathologic fistula healing are established.

Stage 2: Patients will be monitored via EchoSure ultrasound in addition to the standard of care currently followed by the surgeon. Decisions will be made by the vascular surgeon, using a combination of clinical data and the EchoSure data to determine if and when interventions need to be made to prevent failure of fistula maturation. We will then calculate the effect of the EchoMark and EchoSure on the rate of successful fistula maturation.

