Patients are free to withdraw consent at any time. Patients who wish to terminate their participation in the research will no longer receive EchoSure ultrasound examinations of their fistula and their data will be removed from the study.

8: STATISTICAL ANALYSIS

Stage 1:

We will recruit 60 patients for participation in this study who are planning to undergo elective construction of upper extremity autogenous hemodialysis access. The minimum sample size of 45 was determined assuming a 50% successful fistula maturation rate (based on past studies) to yield sufficient power to detect a difference in maturation between this cohort and the intervention cohort in the next aim. It also accounts for the quantity of patient volumes needed to develop a [REDACTED] based on our experience with EchoSure. Lastly, this provides sufficient power to detect a difference in fistula maturation success based on the flow rate (logistic regression power estimation; $\alpha = 0.05$, $\beta = 0.8$, OR 2.5 [from $\text{Pr}(H_0) 0.45$ and $\text{Pr}(H_1) = 0.65$]. As a buffer, based on institutional experience with clinical research and subject attrition a drop-out rate of 25% has been added to yield a total of 60 patients.

Using the EchoSure-derived conduit diameter and volumetric flow as observed values and Duplex-derived conduit diameter and volumetric flow as accepted values, the accuracy of EchoSure will be calculated. Logistic regression will be used to assess the correlation between successful maturation and EchoSure-derived values for flow and conduit diameter at two weeks. Cut points will be evaluated to establish EchoSure criteria for [REDACTED] [REDACTED]. Pearson's correlation will be performed on both EchoSure-derived and Duplex-derived values of volumetric flow and conduit diameter to determine correlation between EchoSure findings at two weeks and both EchoSure and Duplex findings at six weeks.

Stage 2:

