For this portion of the study, we will recruit an additional 60 patients planning to undergo elective construction of upper extremity autogenous hemodialysis access. Again, the EchoMark fiducial marker will be inset at the time of fistula creation. The minimum sample size of 45 (60 prior to 25% dropout factor) is powered to detect an approximate 25% reduction in all-cause fistula failure in the early postoperative period. A χ^2 power analysis was performed with $\alpha = 0.05$, $\beta = 0.8$ and standard-of-care fistula maturation success at 50% based on institutional experience and prior literature which ranges from 30-70% and EchoSure early intervention success based on the Muray-Cases results which showed a 78% success rate achieved by a novel program of pre-maturation ultrasonography and early intervention.

The nominal-by-interval association coefficient, Eta, will be calculated to determine the correlation between successful, unassisted maturation and EchoSure-derived values for flow and conduit diameter at two weeks. This will be compared to the similar findings of stage 1 using Student's t-testing and will validate the early maturation criteria derived from there. The association coefficient will be calculated to determine the correlation between successful, assisted maturation and EchoSure-derived values for flow and conduit diameter immediately following intervention. Pearson's correlation will be performed on both EchoSure-derived and Duplex-derived values of volumetric flow and conduit diameter to determine correlation between findings immediately following intervention and those at six weeks. [REDACTED]

Using χ^2 testing between the stage 1 and 2 cohorts, the benefit to maturation success of intervention based on early postoperative EchoSure examination will be determined.

9: PATIENT ENROLLMENT AND CONSENT

Method of Subject Identification and Recruitment

Patients will be identified and recruited by the surgeons participating in the study. Patients who have been scheduled for a fistula creation surgery will be identified as appropriate for study recruitment. The study details will be explained to identified patients and the consent process will begin for willing patients.

Informed Consent

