10. STUDY PROCEDURES AND METHODS

Patients undergoing fistula creation procedures will be identified. The study will be explained to these patients and informed consent for participation in the study will be obtained from willing patients. A small, FDA-approved tissue marker will be implanted prior to closure of wounds following the Instructions for Use on the FDA-approved labelling.

Stage 1: The fistula will be assessed with intermittent EchoSure examinations, sometimes during routine dialysis visits (maximum 3x/week) to minimize travel. This will conclude when the fistula has entirely matured and the patient begins hemodialysis via the fistula or when the vascular surgeon declares that the fistula has failed despite any and all salvage attempts.

Stage 2: Similar to stage 1 but with implementation of the normative values for relevant variables that resulted from the data collected in stage 1, with subsequent use of the EchoSure flow information in the vascular surgeon's decision making. This stage will also conclude when a year has passed and the fistula is functioning or when the vascular surgeon declares that the fistula has failed despite any and all salvage attempts or that monitoring is no longer clinically necessary.

Actions to Be Taken by Site Staff	Screening and pre-operative evaluation	Clinic Visits	Initiation of dialysis or fistula failure
Consenting	X		
Initial Enrollment Form		X	
Nurse Scan Form		X	
EchoSure Scan		X	
Standard Clinical Exam		X	
End of Trial Period Form			X

11: DATA COLLECTION, ANALYSIS, AND MONITORING

Adverse events are not expected in this study. Unanticipated problems will be reported and discussed with the principal investigator and research coordinator. Patients will be regularly monitored for signs of infection, inflammation or device extrusion. Should the implantable device require removal, it will be removed, and patient will be monitored with conventional methods. The research team will periodically review its protocols to ensure maximal patient safety and data validity.

Source Documentation

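### The planned t-test of the Stage 2 Eta against Stage 1 would not validate the early maturation cut points, because on either reading of the sentence the cut points are never tested

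*Combined protocol and SAP*

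**What the plan says.** In Stage 1 (section 8), "Logistic regression will be used to assess the correlation between successful maturation and EchoSure-derived values for flow and conduit diameter at two weeks". The criteria themselves are thresholds: "Cut points will be evaluated to establish EchoSure criteria for", after which the text is blacked out. Section 8 does not define successful maturation for Stage 1. Section 10 ends Stage 1 follow-up at dialysis through a mature fistula, or when "the vascular surgeon declares that the fistula has failed despite any and all salvage attempts".

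In Stage 2 (section 8), Eta is used to "determine the correlation between successful, unassisted maturation and EchoSure-derived values for flow and conduit diameter at two weeks". The next sentence reads: "This will be compared to the similar findings of stage 1 using Student's t-testing and will validate the early maturation criteria derived from there". Assisted maturation is handled separately, using values taken just after intervention: "The association coefficient will be calculated to determine the correlation between successful, assisted maturation and EchoSure-derived values". More text is blacked out near the end of the Stage 2 analysis.

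On Stage 2 care, section 6 has the surgeon "using a combination of clinical data and the EchoSure data to determine if and when interventions need to be made". Section 10 describes Stage 2 as resembling Stage 1 but "with implementation of the normative values for relevant variables that resulted from the data collected in stage 1".

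Showing that the Stage 1 criteria hold up is a design aim of Stage 2 in section 3. It is not among the Stage 2 endpoints in sections 3 and 5.

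**The concern.** The quoted sentence is the only visible method for a stated aim of Stage 2, and it announces the conclusion in advance. A cut point is validated by applying it unchanged to new patients and counting how many fistulas it classifies correctly. Comparing a measure of association between two cohorts does not do this, and neither does comparing mean flow. The visible text does not apply the Stage 1 cut points to Stage 2 patients, and it gives no rule for deciding that they passed.

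Two further features weaken the comparison. The outcome may differ between the stages. In Stage 2 the scan values also help decide who is treated, so the link between those values and unassisted maturation is partly a product of treatment.

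What is at stake is a report that calls the criteria validated when their classification of new fistulas was never examined.

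**Working it through.** **Inputs from the plan (section 8).** 45 evaluable per stage, 60 enrolled; alpha 0.05; power 80% (printed as beta = 0.8); maturation 50% against 78%; Stage 1 probabilities 0.45 and 0.65.

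**Assumed here.** Standard-normal flow, a logistic outcome with 50% success at mean flow, and an odds ratio per SD of (0.65/0.35)/(0.45/0.55) = 2.27. The plan prints 2.5 and does not say per what unit. Sensitivity means the share of failures flagged by low flow.

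**1. The plan's own figure.** Two proportions, two-sided, no continuity correction, mean proportion 0.64:

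n = [1.96·√(2·0.64·0.36) + 0.8416·√(0.50·0.50 + 0.78·0.22)]² / 0.28² = (1.3305 + 0.5465)² / 0.0784 = 44.9, so 45; and 45/0.75 = 60.

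The figure reproduces, but it sizes only the chi-square comparison. No power or margin is given for the Eta comparison.

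**2. If the Etas are compared.** For a binary outcome Eta is the absolute point-biserial correlation. Each stage gives one value per predictor, so there is no sample of Etas to average. Substituting Fisher z:

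- SE = √(1/42 + 1/42) = 0.218, so significance needs a difference of 1.96 × 0.218 = 0.43 on the z scale.
- A fall from 0.5 to 0.2 gives (0.549 − 0.203)/0.218 = 1.59, and power is about 36%.
- If Stage 1 Eta is 0.50, any Stage 2 value from about 0.12 to 0.75 is not significantly different.

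**3. If the raw two-week values are compared.** When the flow distributions match, the t-test is non-significant in 95% of trials whether or not flow predicts maturation. With 45 per stage it detects a mean shift of 0.5 SD with power 0.65, and of 1 SD with power 0.997. It can therefore reveal a shift in flow, but it carries no information about prediction.

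**4. Eta does not depend on the cut point.** Cut at the Stage 1 40th percentile; Stage 2 flow reads higher, with the same within-stage association and no treatment.

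| Shift in Stage 2 flow | Eta | Flagged | Sensitivity | Specificity |
|---|---|---|---|---|
| 0 | 0.36 | 40% | 54% | 74% |
| 0.5 SD | 0.36 | 23% | 33% | 88% |
| 1 SD | 0.36 | 11% | 17% | 96% |

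Eta is also unsigned: reversing the association leaves it unchanged.

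**5. Effect of treatment guided by the scan.** Assume 25–50% of fistulas are flagged by flow alone and 50–100% of those are treated. In large samples:

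- A marker with true Eta 0 shows 0.16–0.46 if treated fistulas count as not unassisted, and about 0 if they are excluded.
- A marker with true Eta 0.36 shows 0.43–0.62 or 0.21–0.35 respectively.

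The visible text does not say which handling applies.

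**6. The same bias affects a direct test of the cut points.** Take a useless marker with 50% underlying success and 40% flagged, all of them treated. In percent of patients:

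- *Treated classed as failures:* failures are 40 + 30 = 70 and successes 30, all unflagged. Sensitivity is 40/70 = 57%, specificity 100%, and AUC = 4/7 + ½·3/7 = 0.79.
- *Treated excluded:* no flagged fistula remains, so sensitivity is 0/30 = 0%.
- *Half of the flagged treated:* failures are 20 + 10 + 30 = 60, of which 30 are flagged; successes are 40, of which 10 are flagged. AUC = 0.75·0.5 + ½(0.25·0.5 + 0.75·0.5) = 0.625. With the treated excluded, sensitivity is 10/40 = 25%.

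**The case against.** **The test can be repaired.** Two coefficients can be compared using their standard errors, Fisher z or a bootstrap, and an Eta could be computed from Stage 1 data even though the visible text names none. This stands. The fault is that the ordinary t-test does not apply as described, not that no comparison is possible. A valid comparison would still leave the cut points untested.

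**The outcomes may be the same.** A reader might infer that the two stages definitely use different outcomes. The documents do not support that. Stage 1 success is undefined, and the reference to similar Stage 1 findings may imply a common definition. Because Stage 1 allows salvage, the outcomes may differ, and no more can be said.

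**The raw-value reading has some merit.** It would often detect the kind of shift that moves a cut point's performance. This is true, but a matching mean does not show that low flow predicts failure.

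**Pass rates depend on an unstated rule.** A reader might infer that a worthless criterion would usually be declared valid. With 45 per stage, Fisher z and no treatment, reading a non-significant difference as validation passes one in about 84% of trials (78% at odds ratio 2.5; about 76% among trials with a significant Stage 1 association). If a significant Stage 2 Eta is also required, the figure is about 5%. The plan states neither rule, so these are illustrations only. Section 4 also reports two-week flow and diameter as significant predictors in more than 500 fistulas, which makes a worthless marker less plausible.

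**Blacked-out text may hold a cut-point check.** It may, so total absence cannot be claimed. It would not make the visible sentence valid.

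**Conclusion.** The point holds and should be fixed. Whichever quantity the t-test compares, the result cannot validate the Stage 1 criteria: Eta has no sign and does not depend on the cut point, and a test of raw values leaves maturation out. The possible difference in outcome definition and the treatment guided by Stage 2 scans add to the problem, but the conclusion does not need them.

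The sizes are illustrative. The fall in sensitivity from 54% to 33% at an unchanged Eta of 0.36 rests on an assumed odds ratio per SD, an assumed cut point and an assumed shift. The treatment figures rest on assumed fractions flagged and treated.

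A reader might extend the criticism to the chi-square comparison of maturation between stages. It does not reach that far: that test uses neither Eta nor the cut points, and its sample size reproduces. Validation of the criteria is a design aim rather than a listed endpoint, which limits the severity.

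**What to change.** - Delete the Eta and t-test validation sentence. Say that Stage 2 will describe the performance of the criteria, not validate them.
- Lock the Stage 1 cut points before the first Stage 2 enrolment and apply them unchanged to the Stage 2 two-week scans. Report sensitivity, specificity, PPV, NPV and AUC with 95% confidence intervals.
- State one outcome definition, assisted or unassisted, and use it in both stages.
- Take the main evidence on predictive performance from Stage 1, with bootstrap correction for optimism.
- Show Stage 2 results with intervened fistulas classed as failures and with them excluded, as a sensitivity display only. State that both are biased whenever flagged fistulas are treated because of the scan, not only when most are, and that Stage 2 alone therefore cannot validate the criteria.

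**Cost.** Mainly analysis text, a more modest conclusion and wide intervals. The expected width should not be worked out from the 78% success rate: that figure is success under early intervention and fits neither way of handling intervened fistulas. Section 8 already calls for two-week values and the assisted/unassisted split, but the section 10 schedule lists only clinic visits. Confirm that the two-week scan and every intervention are recorded; if they are not, the visit schedule or case report form needs a small change.

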Hemodialysis access is a conduit through which dialysis machinery may be connected to the patient's circulatory system. The creation and maintenance of access constitutes a significant portion of dialysis costs. A fifth of all ESRD hospitalizations are attributable to access complications. Current clinical practice guidelines maintain that an autogenous arteriovenous (AV) fistula is the ideal vascular access conduit for hemodialysis (Figure 1).(6) Fistulae are superior to prosthetic grafts insofar as they require fewer interventions to maintain patency, have a far lower rate of failure and infection and a longer usable lifespan. Indwelling central venous catheters have the highest risk of death, infection and cardiovascular morbidity.(7) Autogenous AV fistulae confer a mortality benefit when used for dialysis.(1) In the United States, 63% of patients on dialysis use fistulae.(6)

The primary limitation of AV fistulae is the high rate of failure. Between 30%-70% of fistulae suffer primary failure and are never used because they have failed to mature or adapt into suitable dialysis access.(1) This failure nearly always results in a delay in dialysis initiation and requires placement of a dialysis catheter in addition to another surgery for access creation. The financial burden of a failure to mature is accordingly substantial. Dialysis-related expenses incurred by patients in their first year of renal failure are 23% lower if dialysis is started in a mature fistula than without.(8) Techniques to maximize the rates of maturation hold substantial potential for cost savings. Muray-Cases et al. demonstrated that a program of pre-maturation ultrasonography and intervention resulted in a maturation success rate of 78% at the time of dialysis.(9) Notably, the study involved exclusively distal radiocephalic fistulas, a type that has a typical historical rate of maturation failure between 50-70%.(10) Currently, resource limitations enable reimbursed performance of a Duplex ultrasound if maturation is not present at six weeks. Ultrasound surveillance of the maturing fistula in the early postoperative period is not typically performed as CMS and local coverage determination criteria require clinical indications that cannot apply in the early postoperative period. This 'blind period' immediately after fistula creation holds substantial potential for improvement of care.

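### The Stage 2 benefit rests on an unadjusted chi-square between sequential cohorts, so a change in fistula-type mix between stages would enter the estimated effect

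*Combined protocol and SAP*

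**What the plan says.** Section 6 describes the design: "This is a prospective, single arm, non-randomized, multi-center observational study to record objective data". Stage 2 has to follow Stage 1, because section 10 defines it by "implementation of the normative values for relevant variables that resulted from the data collected in stage 1". Its patients are new: section 8 says "we will recruit an additional 60 patients planning to undergo elective construction of upper extremity autogenous hemodialysis access".

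The Stage 2 primary endpoint is the maturation (or failed maturation) rate. Section 8 tests it by χ² "testing between the stage 1 and 2 cohorts, the benefit to maturation success of intervention based on early postoperative EchoSure examination will be determined". The sample size rests on the same comparison. It takes "standard-of-care fistula maturation success at 50" per cent against 78% in Stage 2, which gives 45 evaluable and 60 enrolled patients per stage.

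The readable text names no covariate, stratum, matching or sensitivity analysis for this test. The logistic regression in section 8 belongs to Stage 1 and relates maturation to two-week flow and diameter; it does not compare stages. Sections 3 and 7 admit any upper-extremity autologous fistula, with no cap or stratum by type. On distal radiocephalic fistulas, section 4 says: "a type that has a typical historical rate of maturation failure between 50-70" per cent. For fistulae overall it gives 30–70%.

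**The concern.** A chi-square between two cohorts keeps its nominal error rate only if both would have the same expected maturation without the EchoSure-guided decisions. Randomisation would secure that on average, but here nothing does. Stage 2 patients are enrolled later and chosen by surgeons who by then have the Stage 1 criteria, and the mix of fistula types is left free.

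If type is prognostic, a change in mix between stages passes straight into the difference that the plan calls the benefit. A falling radiocephalic share would look like an EchoSure effect. A rising share would mask a real one.

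**Working it through.** **1. The plan's own figure.** With success rates of 0.50 and 0.78, mean 0.64, two-sided α 0.05 and power 0.80 (the plan prints β = 0.8, evidently meaning power):

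n = [1.960 × √(2 × 0.64 × 0.36) + 0.842 × √(0.50 × 0.50 + 0.78 × 0.22)]² / 0.28² = [1.960 × 0.679 + 0.842 × 0.649]² / 0.0784 = 44.9, so 45 per stage.

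45 / 0.75 = 60. The stated sample size reproduces and presumes comparable cohorts.

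**2. Bias from a change in mix.** With no true effect:

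spurious difference = (radiocephalic share in Stage 1 − share in Stage 2) × (success of other types − success of radiocephalic).

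**3. Inputs.**
- 45 per stage and α 0.05: section 8.
- Radiocephalic success 40%: assumed, the middle of the 30–50% implied by section 4.
- Success of other types 60% or 70%: assumed. The documents give no rate for other types; 70% is the favourable end of the overall range.
- Radiocephalic share centred on 67%: assumed. With other types at 70% it gives 0.67 × 0.40 + 0.33 × 0.70 = 0.499, matching the plan's 50%.
- Size of the shift: assumed, 0 to 40 points.

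**4. Rejection rate with no true effect** (crude χ² by exact binomial enumeration, without continuity correction; Mantel-Haenszel by simulation):

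| Share, Stage 1 → 2 | Other types 60%: bias, crude error | Other types 70%: bias, crude error | Stratified by type |
|---|---|---|---|
| 67% → 67% | 0 points, 4.5% | 0 points, 4.5% | about 5% |
| 72% → 62% | 2 points, 4.9% | 3 points, 5.4% | about 5% |
| 77% → 57% | 4 points, 6.1% | 6 points, 8.1% | about 5% |
| 82% → 52% | 6 points, 8.1% | 9 points, 12.7% | about 5% |
| 87% → 47% | 8 points, 11.0% | 12 points, 19.4% | about 5% |

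Example: 0.20 × (0.70 − 0.40) = 0.06, or 6 points. With other types at 70%, the chance of a false finding in favour of EchoSure is 2.3% with no shift and 7.6%, 12.5% and 19.3% at 20, 30 and 40 points.

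**5. Sensitivity to the radiocephalic rate.** With other types at 70% and the share falling from 60% to 40%, radiocephalic success of 50%, 40% or 30% gives a bias of 4, 6 or 8 points and a crude error of 6.5%, 8.2% or 10.9%.

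**6. The opposite direction.** Suppose a true effect of the planned size: radiocephalic 40% to 70%, other types 70% to 94%. If the share rises from 57% to 77%, expected success is 0.57 × 0.40 + 0.43 × 0.70 = 0.529 in Stage 1 and 0.77 × 0.70 + 0.23 × 0.94 = 0.755 in Stage 2. The apparent gain is 22.6 points instead of about 28. Crude power falls from 81% to 62%, while stratified power is about 80–81%. With an equal mix, power is 83% stratified and 81% crude, so stratification costs nothing.

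**7. Room for adjustment.** Expected failures at the planned rates are 45 × 0.50 + 45 × 0.22 = 22.5 + 9.9, about 32. At ten events per parameter this carries about three: stage plus two others.

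**The case against.** The case against has substance.

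- **Strength of the type effect.** A reader might infer that the protocol itself says maturation depends strongly on fistula type. It does not. The two ranges in section 4 overlap, share an upper end, and the overall range contains the radiocephalic one. Prognostic weight is a reasonable inference and no more.
- **Size of the shift.** Nothing in the documents predicts a shift of 20 to 40 points. Chance imbalance is already covered by the nominal error rate; only a systematic change inflates it. With a constant share of 67%, the standard error of the observed gap is √(2 × 0.67 × 0.33 / 45) = 0.099, so a 40-point gap would be about four standard errors. At a 10-point shift the harm is negligible.
- **Sites and surgeons.** A reader might infer that these will differ between stages, since section 6 says "Patients will be identified and recruited by the surgeons participating in the study, who will be determined at a later date" and section 3 leaves the number of sites open. Not yet named is not the same as different by stage, and no site-specific rates are given. If sites did differ wholly by stage, site would be aliased with stage: every site stratum would lack a comparison, and no model could separate the two.
- **Redaction.** Text is blacked out immediately before the χ² sentence, so an adjustment described there cannot be excluded.
- **Stratified error near 5%.** This follows from the set-up, in which type is the only confounder. Stratifying by type does not protect against others.

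What survives is narrower. As far as it can be read, the plan makes an unadjusted test between sequential cohorts the arbiter of benefit and leaves free a factor that its own background suggests may matter.

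**Conclusion.** The concern holds for fistula type, with moderate confidence. An unadjusted chi-square between sequential, non-randomised cohorts does not isolate the effect of EchoSure-guided intervention, and a systematic change in type mix would bias it in either direction. Under the stated assumptions, the crude error is about 5% at a 10-point shift in radiocephalic share, 6–8% at 20 points, 8–13% at 30 and 11–19% at 40. The upper figures need both a large systematic shift and a 30-point difference in success between types, neither of which the documents establish.

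A reader might go further and infer that any observed benefit will be spurious, or that adjusting for site or surgeon would settle the matter. The documents support neither. The sample-size arithmetic is sound, and site adjustment works only where the same sites enrol in both stages.

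A further stage difference bears on the same test. Section 3 describes monitoring for 24 weeks, then in a second entry, also labelled Stage 1 but apparently meant for Stage 2, for up to 52 weeks. Section 7 follows Stage 1 until the fistula matures or is judged non-salvageable. Unequal windows could shift the maturation rate on their own, and adjustment for type would not remove that.

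**What to change.** 1. Make the primary stage comparison a Mantel-Haenszel test stratified by fistula type (radiocephalic v other), or a logistic model with stage and type reported as a standardised risk difference with 95% CI. Specify it before Stage 2 outcomes are seen.
2. Record fistula type on the enrolment form in both stages. The minimum data list in section 11 does not name it.
3. Keep the crude chi-square as a supporting analysis, and tabulate type mix by stage.
4. Add site, pooling small ones, only if the same sites enrol in both stages. About 32 expected failures will not carry many site terms.
5. Replace the sentence that the benefit will be determined with one saying that the adjusted difference is estimated against a non-concurrent cohort.
6. Reconcile the follow-up descriptions in sections 3 and 7, so that it is clear over what period maturation is counted in each stage.

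The cost is SAP wording, a small change in data capture and a little analysis; the sample size does not change. Time trends and unmeasured differences between the cohorts remain, which is why the change in wording is needed as well as the adjustment.
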